1.1 RATIONALE FOR THE STUDY

VRC's clinical development plans for neutralizing MAbs include potential uses in three broad areas: 1) prevention of mother-to-child transmission (MTCT) of HIV, 2) prevention of sexual transmission of HIV, and 3) therapeutic application in HIV-1 infected individuals. The initial development plan focused on clinical research to lead to an efficacy evaluation of VRC01 for MTCT of HIV. To evaluate the safety of administering VRC01 to infants who may be HIV-infected at birth, studies in infants were preceded by Phase 1 trials in HIV-infected adults (VRC 601) and HIV-uninfected adults (VRC 602) that began in 2013 and 2014, respectively.

VRC01 has been assessed as safe and well tolerated at the 5-40 mg/kg doses administered intravenously (IV) and at 5 mg/kg subcutaneously (SC) in both HIV-infected and HIV-uninfected adult populations. The pharmacokinetic (PK) parameters of passively administered VRC01 were also evaluated. For healthy adults who received VRC01 at the 5-40 mg/kg doses administered IV (n=18), the clearance was 0.016 ± 0.003 L/h and an overall mean value for the elimination half-life was 15.4 ± 3.9 days for IV administration. At 5 mg/kg SC (n=5), the clearance was 0.029 ± 0.007 L/h, and the mean elimination half-life was 16.6 ± 2.9 days. Work is ongoing to further describe the PK and biological activity of VRC01 after repeat dosing in HIV-infected and -uninfected adults.

VRC07-523LS, an engineered variant of VRC07 that was discovered in the same HIV-1 infected subject as VRC01, neutralizes more HIV envelope strains than VRC01 at lower concentrations.

VRC07-523LS was found to be 5-to 8-fold more potent than VRC01, with an inhibitory concentration $IC_{50} < 50$ mcg/mL against 96% of HIV-1 pseudoviruses representing the major circulating HIV-1 clades and $IC_{50} < 1$ mcg/mL against 92% of HIV-1 viruses tested and displayed minimal levels of autoreactivity. VRC07-523LS was shown to have a prolonged half-life over VRC07 by about 2-fold [3].

In vivo proof-of-concept studies showed that VRC07-523LS is about 5-fold more potent than VRC01LS in Rhesus macaques and displays a longer half-life (9.8 days) than VRC07 (4.9 days) after a single dose of MAb at 10 mg/kg administered IV [3].

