6.2 OBJECTIVES

The primary objective is to evaluate the safety and tolerability of VRC07-523LS administered at 1 mg/kg IV, 5 mg/kg IV, 5 mg/kg SC, 20 mg/kg IV and 40 mg/kg IV as a single dose, and administered at 20 mg/kg IV and 5 mg/kg SC by repeat dosing every 12 weeks for a total of 3 product administrations to healthy adults. Secondary objectives include evaluation of the PKs at each dose level through 24 weeks after the last dose and testing for the presence of ADA against VRC07-523LS. Exploratory objectives include determining if measurable levels of VRC07-523LS can be found in oral secretions, evaluation for evidence of functional activity of VRC07-523LS in collected samples, and evaluation of allotype-specific effects on the VRC07-523LS pharmacokinetics.

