6.4.5 Pharmacokinetics Analysis

Blood samples for PK evaluations will be collected at timepoints per the Schedule of Evaluations.

Individual Subject Pharmacokinetic Analysis: A non-compartmental PK analysis will be performed using Phoenix (Centara) or a similar program on the VRC07-523LS concentration data generated from each subject. Calculated PK parameters for IV Groups 1, 2, 4, 5, and 7 will include: area-under-the-curve (AUC), maximum concentration (Cmax), time to Cmax (Tmax), clearance (CL), volume of distribution (Vdz), terminal elimination rate constant (λz) and the terminal half-life ($T_{1/2}$). For Groups 3 and 6, the PK parameters will include AUC, Cmax, Tmax, apparent clearance (CL/F), apparent volume of distribution (Vdz/F), λz and $T_{1/2}$. Cmax and Tmax will be taken directly from the observed concentration-time data. The terminal slope, λz , will be determined from the log-linear portion of the curve and the $T_{1/2}$ calculated as $0.693/\lambda z$. $AUC_{0-Clast}$ will be determined using the linear trapezoidal method, where C_{last} is the concentration at 12 weeks after the first two doses in Groups 6 and 7 and the concentration at 24 weeks after dose in Groups 1, 2, 4 and 5 and final dose in Groups 6 and 7. If the final sample (C_{last}) has measurable VRC07-523LS concentrations, the remaining AUC after the final concentration ($AUC_{Clast-inf}$) will be estimated as $Clast/\lambda z$. Data will be summarized based by each dose group and overall for IV administration

groups for CL, Vd and $T_{1/2}$. For Groups 6 and 7, potential accumulation will be assessed as the ratios of the $AUC_{0-\infty}$ and C_{max} for the first and the last doses. The potential for non-linearity PKs among IV groups will be determined by comparing the dose-adjusted ratios for C_{max} and AUC between IV groups. Additional compartmental analysis will be performed as warranted by the data.

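### The linear trapezoid over 28-day sampling gaps makes first-dose CL slightly but systematically low, and the dose that supplies CL in the repeat-dose groups is not named

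*Combined protocol and SAP*

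**What the plan says.** All of this is in Section 6.4.5, Pharmacokinetics Analysis, in the paragraph on individual-subject analysis.

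- AUC to the last concentration "will be determined using the linear trapezoidal method". No logarithmic rule is given for the declining limb.
- The last concentration, Clast, "is the concentration at 12 weeks after the first two doses in Groups 6 and 7". It is at 24 weeks after the dose in Groups 1, 2, 4 and 5, and after the final dose in Groups 6 and 7.
- If the final sample "has measurable VRC07-523LS concentrations, the remaining AUC after the final concentration" is estimated as Clast/λz. No correction for drug left from earlier doses is mentioned.
- The list that opens "Calculated PK parameters for IV Groups 1, 2, 4, 5, and 7 will include" contains CL and Vdz. The list for Groups 3 and 6 contains CL/F and Vdz/F. Neither gives a formula for CL or names the dose that it comes from.
- "Data will be summarized based by each dose group and overall for IV administration" groups, for CL, Vd and half-life.
- In Groups 6 and 7, "potential accumulation will be assessed as the ratios of the" AUC to infinity and Cmax for the first and last doses.
- Possible non-linearity is judged by comparing dose-adjusted Cmax and AUC between IV groups.

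The schedules in Appendix III put the PK draws after week 4 at 28-day steps. Section 6.2 has the repeat-dose groups treated "by repeat dosing every 12 weeks for a total of 3 product administrations".

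**The concern.** There are two separate issues.

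**Integration rule.** When concentrations fall exponentially, the chord between two samples lies above the curve, and the excess grows with the gap relative to the half-life. AUC is then overstated and CL understated after every first dose. The size depends on half-life, so it differs between subjects, and adding subjects does not average it away.

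**Source dose.** AUC to infinity after dose 3 still contains drug from doses 1 and 2. That is what the accumulation ratio is meant to show, but the same AUC cannot serve as the denominator of Dose/AUC. Nothing in the section prevents this use. If it happened, Groups 4 and 7, both given 20 mg/kg IV, could show different CL for purely arithmetic reasons. The error would carry into Vdz, the pooled IV summary and the dose-adjusted AUC comparison.

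**Working it through.** The documents state no AUC, CL or bias figure, so there is nothing to reproduce.

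**Inputs**
- Half-life: Section 1.1 reports, for VRC01, "an overall mean value for the elimination half-life was 15.4 ± 3.9 days for IV administration". It gives no human value for VRC07-523LS, only a gain of about 2-fold over VRC07 in animals. Assumed values are 15.4 days, about 31 days (2 × 15.4 = 30.8) and 40 days as an upper value with no source in the documents.
- Dosing interval: 84 days, three doses.
- CL formula: assumed to be Dose/AUC0-inf, because none is stated.
- Spread of CL: VRC01, Section 1.1, 0.003/0.016 = about 19%.

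**1. Trapezoid, one interval.** With k = ln2/half-life and gap h, the linear rule multiplies the true area by x/tanh(x), where x = kh/2. For h = 28 days:

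| Half-life | x | Factor |
|---|---|---|
| 15.4 d | 0.630 | 1.129 |
| 31 d | 0.313 | 1.032 |
| 40 d | 0.243 | 1.020 |

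**2. Trapezoid, whole profile.** For one-compartment decline on Schedule 1 at 15.4 days, 28.4% of AUC lies beyond day 28. The 28-day gaps therefore add about 0.284 × 12.9% = 3.7%, and the shorter gaps before day 28 add about 0.5%. The total is +4.1%, so CL is 1/1.041 − 1 = −3.9%. The same sum gives −1.7% at 30.8 days and −1.1% at 40 days.

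The plan expects two compartments. Assuming a distribution half-life of 2 days and half the initial concentration in the fast phase, CL on Schedule 1 is −5.0% at 15.4 days, −2.4% at 30.8 days and −1.7% at 40 days. A fast-phase fraction of 0.6 lowers these by roughly another 0.3 to 0.5 points.

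First-dose error over 15.4 to 40 days, across the assumed profiles (SC absorption rate 0.15 to 1.0 per day):

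| Groups | Linear rule | Linear-up/log-down |
|---|---|---|
| 1, 2, 4, 5 (IV) | −1.1 to −5.0% | 0 to −1.2% |
| 7, dose 1 (IV) | −0.8 to −5.6% | 0 to −1.2% |
| 3 (SC) | −0.5 to −3.5% | +0.2 to +2.2% |
| 6, dose 1 (SC) | −0.3 to −3.8% | +0.2 to +2.2% |

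**3. Carry-over, if CL were taken after dose 3.** With r = exp(−84k), AUC0-inf after dose 3 is the single-dose AUC times 1 + r + r². The error in Dose/AUC is 1/(1 + r + r²) − 1:

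| Half-life | r | 1 + r + r² | CL error |
|---|---|---|---|
| 15.4 d | 0.023 | 1.023 | −2.3% |
| 31 d | 0.153 | 1.176 | −15.0% |
| 40 d | 0.233 | 1.288 | −22.3% |

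Under the full written rule, Group 7 dose 3 at 30.8 days is −16.3% (one compartment) to −17.3% (two). Log-down alone leaves −14.8% to −15.3%, so changing the integration rule does not cure this part.

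**4. Pooled IV CL.** Planned IV subjects number 3 + 3 + 3 + 3 + 5 = 17, of whom Group 7 supplies 5. If all five values came from dose 3, the pooled mean would shift by 5/17 × 15.0% = 4.4% at 31 days and 5/17 × 2.3% = 0.7% at 15.4 days.

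**The case against.** The strongest reply is that the larger figures describe something the plan never says it will do. AUC to infinity after the last dose is called for only in the accumulation ratio, where carry-over is the quantity of interest. With dosing every 84 days, AUC to Clast at 12 weeks is already a dosing-interval AUC for doses 1 and 2. The population-PK paragraph of the same section estimates CL in NONMEM without a trapezoid or this extrapolation, tests first against later doses as an effect on CL, and supplies the model for the dosing simulations. All of this stands, and it makes the second issue a missing specification, not a demonstrated bias.

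The first-dose error is also small. With a 19% spread, the standard error of a three-subject mean is about 19%/√3 = 11%, and Section 6.3.2 calls the study primarily descriptive. That limits the weight of the point. It does not justify keeping a rule with a known one-directional error when a better one is a software option.

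A reader might also infer three stronger things that the documents do not support:
- That extrapolation to infinity biases CL in every group. After a single dose, adding Clast/λz is correct; only the trapezoid contributes error there.
- That repeat-dose CL must always be worse. For SC dosing at 15.4 days with fast absorption (1.0 per day), dose 3 is −3.5% against −3.8% for dose 1.
- That the worst cases add up. The trapezoid error is largest at short half-lives and the carry-over at long ones.

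**Conclusion.** The point holds in a limited form. As written, the linear rule understates first-dose CL by about 1 to 5% in the IV groups (5.6% at the extreme for Group 7) and CL/F by up to about 4% in the SC groups, over assumed half-lives of 15.4 to 40 days. The direction is consistent and the size varies with half-life.

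The source dose for CL and CL/F in Groups 7 and 6 is unspecified. Only if dose 3 were used with Dose/AUC0-inf would CL be about 2%, 15% or 22% low at 15.4, 31 or 40 days, and the pooled IV CL about 4% low at 31 days. It would be wrong to conclude that the plan will report a false fall in CL with repeat dosing, or that its population-PK results and simulations are compromised.

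The figures rest on assumed half-lives above 15.4 days, assumed distribution and absorption values, an assumed CL formula, and sampling times read from the Appendix III tables.

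**What to change.** Two edits to Section 6.4.5:

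1. Replace the linear trapezoidal method with the *linear-up/log-down trapezoidal method*.
2. Add: *In Groups 6 and 7, CL (CL/F) and Vdz (Vdz/F) are derived from the first dose. The overall IV summary and the dose-adjusted AUC comparison use first-dose values. AUC0-inf after the last dose is used only for the accumulation ratio.*

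The cost is a software setting and a few sentences, with no new samples or visits. Two limits should be accepted knowingly. In the SC groups, log-down leaves a small error of the opposite sign (+0.2 to +2.2%). In Groups 6 and 7, first-dose AUC0-inf relies on extrapolation beyond week 12: in the one-compartment IV case the extrapolated share is r, about 2%, 15% and 23% at 15.4, 31 and 40 days. That share should be reported beside CL.

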PSRT	Protocol Safety Review Team
Q	Inter-compartmental clearance
QA	quality assurance
RSC	Regulatory Support Center
SAE	serious adverse event
SC	Subcutaneous
SHIV	simian-human immunodeficiency virus
SST	serum separator tube
TCR	tissue cross reactivity
T _½	half-life
Tmax	time of maximal concentration (C _{max})
UNAIDS	Joint United Nations Programme on HIV/AIDS
UP	unanticipated problem
USP	United States Pharmacopeia
V _d	volume of distribution
VRC	Vaccine Research Center
WBC	white blood cell

PRÉCIS

VRC 605: A Phase 1 Dose-Escalation Study of the Safety and Pharmacokinetics of a Human Monoclonal Antibody, VRC-HIVMAB075-00-AB (VRC07-523LS), Administered Intravenously or Subcutaneously to Healthy Adults

Study

Design:

This is the first study in healthy adults of the VRC-HIVMAB075-00-AB (VRC07-523LS) monoclonal antibody (MAb). It is a dose-escalation study to examine safety, tolerability, dose, and pharmacokinetics of VRC07-523LS. The hypothesis is that VRC07-523LS administration to healthy adults will be safe by the intravenous (IV) and subcutaneous (SC) routes. A secondary hypothesis is that VRC07-523LS will be detectable in human sera with a definable half-life.

Product

Description: VRC-HIVMAB075-00-AB (VRC07-523LS) is a human MAb targeted to the HIV-1 CD4 binding site. It was developed by the VRC/NIAID/NIH and manufactured under current Good Manufacturing Practice regulations at the VRC Pilot Plant operated under contract by the Vaccine Clinical Materials Program, Leidos Biomedical Research, Inc., Frederick, MD. Product is provided at 100 ± 10 mg/mL in a volume of 6.25 ± 0.10 mL filled into 10 mL glass vials.

Subjects: Healthy adults, 18-50 years of age.

Study Plan: This study includes 4 open-label, dose escalations of VRC07-523LS from 1 mg/kg IV to 40 mg/kg IV, 1 route escalation from IV to SC, and 2 open-label groups to assess repeat dosing of VRC07-523LS. Groups will be enrolled per the dose and route escalation and safety evaluation plan.

VRC 605 Study Schema					
Group	Subjects	Administration Schedule			
		Day 0	Week 12	Week 24	
1	3	1 mg/kg IV			
2	3	5 mg/kg IV			
3	3	5 mg/kg SC			
4	3	20 mg/kg IV			
5	3	40 mg/kg IV			
6	5	5 mg/kg SC	5 mg/kg SC	5 mg/kg SC	
7	5	20 mg/kg IV	20 mg/kg IV	20 mg/kg IV	
Total*	25	*The expected enrollment is 25 subjects. Enrollment up to a total of 40 subjects is permitted if additional subjects are necessary for safety or PK evaluations.			

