When administered IV at a single dose of 10 mg/kg in cynomolgus macaques, the half-life of VRC07-523LS was about 12 days, and persisted at least 28 days (last collection point) in rectal and vaginal secretions and tissues. When administered SC at a single dose of 10 mg/kg in rhesus macaques, the half-life of VRC07-523LS was about 14 days and it persisted at least 49 days (last collection point) in rectal, vaginal and nasal secretions. Complete protection from SHIV-SF162P3 challenge was demonstrated with a single dose of VRC07-523LS at 20 mg/kg administered IV.

A repeat dose IV and SC toxicity study with VRC07-523LS was performed in male and female Sprague-Dawley rats in accordance with “Good Laboratory Practice (GLP) for Nonclinical Laboratory Studies.” Treatment with VRC07-523LS at doses up to 400 mg/kg/dose IV or 40 mg/kg/dose SC with three doses at 10 days intervals was generally well tolerated as most findings were reversible and no longer seen at the end of the recovery period. Additionally, histologic changes were not observed in the GLP repeat dose toxicology study in the cell types with staining observed in the GLP tissue cross reactivity (TCR) study.

Increased neutralization potency *in vitro* and prolonged half-life of VRC07-523LS correlate with improved protection against SHIV infection *in vivo* in animal studies, suggesting a potential clinical application against HIV-1 infection in humans in preventive and/or therapeutic settings.

The proposed VRC07-523LS doses are based on human studies of VRC01, preclinical studies of VRC07-523LS and the requirements to assess PK at a range of doses that will allow for full PK analysis and predictive modeling. This range of doses allows for informative PK modeling to be performed with the study data obtained here. Preclinical studies with VRC07-523LS to date also support the proposed human doses and intervals between doses to achieve passive immunity as described in Section 2 and in the Investigator’s Brochure (IB).

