6.3 SIZE AND ACCRUAL

Recruitment will target about 25 healthy adults of age 18-50 with 3 subjects in each dose escalation group (Groups 1-5), and 5 subjects in each repeat dosing group (Groups 6 and 7). The permitted accrual is 40 subjects to allow for additional enrollments in the event that an enrolled subject does not complete the minimum evaluations needed to meet the protocol criteria for the group dose safety or dose escalation evaluation.

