Population Pharmacokinetic Analyses: Population PK analyses will be performed on the VRC07-523LS PK data following IV and SQ administration to determine compartmental PK parameters with the program NONMEM. One and two compartment PK models will be assessed. Based on prior PK studies of antibodies, including VRC01, it is anticipated that a two compartment model will adequately characterize the data. The population analysis will generate estimates for initial and final volumes of distribution (Vd_1 and Vd_2), inter-compartmental clearance (Q), CL and bioavailability (F). Given the small subject numbers, the population PK analysis will not include an exploratory covariate analysis to assess clinical factors as fixed effects associated with VRC07-523LS PK parameters with the exception of dose (5 vs 20 vs 40 mg/kg), and first vs subsequent doses as a fixed effects on CL, Vd_1 , and Vd_2 . The terminal half-life, $t_{1/2\beta}$ will be determined from CL, Vd_1 , Vd_2 and Q. Final model selection will be based on changes in the objective function and graphically by goodness of fit plots. The final population model will be assessed using bootstrap analysis and dose normalized visual posterior predictive check. VRC07-523LS dosing strategies and their ability to achieve and maintain target VRC07-523LS concentrations will be performed using the final population PK model and Monte Carlo simulations with at least 5000 replicates.

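### The check for non-linear IV pharmacokinetics has no interval or overall estimate, and the population dose effect leaves out 1 mg/kg; add a log-log slope beside the ratios

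*Combined protocol and SAP*

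**What the plan says.** Section 6.4.5, in its paragraph on individual-subject analysis, sets out the linearity assessment: "The potential for non-linearity PKs among IV groups will be determined by comparing the dose-adjusted ratios for" Cmax and AUC. It names no pairs of groups, reference dose, model, confidence interval or criterion. The groups concerned follow from the same paragraph ("Calculated PK parameters for IV Groups 1, 2, 4, 5, and 7 will include" AUC, Cmax and the rest). Section 6.3 gives their sizes: "3 subjects in each dose escalation group (Groups 1-5), and 5 subjects in each repeat dosing group (Groups 6 and 7"). Section 1.1 justifies the doses partly by the modelling they permit: "This range of doses allows for informative PK modeling to be performed with the study data obtained here".

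The next paragraph of 6.4.5 plans one NONMEM population model. It rules out covariate exploration "with the exception of dose (5 vs 20 vs 40 mg/kg), and first vs subsequent doses as a fixed effects on CL" and the two volumes. The listed levels do not include 1 mg/kg, although the Précis describes "dose escalations of VRC07-523LS from 1 mg/kg IV to 40 mg/kg IV".

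For AUC, the last concentration "is the concentration at 12 weeks after the first two doses in Groups 6 and 7", whereas the single-dose IV groups are followed to 24 weeks.

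**The concern.** Three of the four IV dose levels have 3 subjects. A ratio of two such means is noisy, and without an interval a reader cannot separate noise from a dose effect. By dose level there are six possible ratios, and no single quantity summarises them. The lowest dose, which supplies most of the 40-fold range, is absent from the listed population dose effect. As written, it therefore enters the linearity question only through these unaccompanied ratios.

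At stake is how the results can be read. Section 6.4.5 reports CL, Vd and half-life by dose group and also overall for IV. The overall summary is easier to interpret if a stated amount of non-linearity can be excluded.

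**Working it through.** **The plan's own figure.** None is given for linearity. The design figures in 6.3.2 concern safety events only.

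**Inputs**
- IV subjects: 3 at 1 mg/kg, 3 at 5, 3 + 5 = 8 at 20 (Groups 4 and 7), 3 at 40; total 17 (6.3, 6.4.5).
- Dose range 1 to 40 mg/kg, ln 40 = 3.689.
- Between-subject CV: not given for VRC07-523LS. Section 1.1 reports for VRC01 that "the clearance was 0.016 ± 0.003 L/h", so 0.003/0.016 = 19%. Using this for VRC07-523LS is an assumption; 15% to 40% is shown below. The 95% two-sided level is also an assumption.

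**Precision of the slope**
1. Mean of ln dose = (3×0 + 3×1.609 + 8×2.996 + 3×3.689)/17 = 2.345. Sum of squares about it, Sxx = 26.93.
2. SE(slope) = σ/√26.93 = 0.193σ, on 15 df. SE of the implied log 40:1 ratio = 0.193σ × 3.689 = 0.711σ.
3. Direct 40-versus-1 ratio of dose-adjusted values: SE = σ√(1/3 + 1/3) = 0.816σ, on 13 df with an SD pooled over the four dose levels, or 4 df with those two groups alone.
4. Variance ratio (0.816/0.711)² = 1.32, so the direct contrast already carries 1/1.32 = 76% of the slope information.
5. Half-widths on the log scale: 2.131×0.711σ = 1.515σ (regression); 2.160×0.816σ = 1.764σ (pooled SD); 2.776×0.816σ = 2.267σ (two-group). Regression is narrower by 14% and by 33%. These percentages do not depend on σ.

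**On the ratio scale**, with σ = √ln(1 + CV²), the 40:1 ratio is known to within a factor of:

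| CV | Regression | Pooled SD | Two-group, 4 df |
|---|---|---|---|
| 15% | 1.25 | 1.30 | 1.40 |
| 19% | 1.33 | 1.39 | 1.53 |
| 25% | 1.45 | 1.54 | 1.75 |
| 40% | 1.79 | 1.97 | 2.40 |

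**How far noise alone goes.** With exactly linear PK and the four dose levels above, simulation shows the largest ratio of geometric means exceeding 1.25 in 39% of trials at CV 19% and 61% at CV 25%. The 1.25 mark is illustrative; the plan has no threshold.

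**Power at CV 19%, 5% two-sided, for dose-adjusted exposure** (slope by simulation; the others from noncentral t and F). Lack of fit compares four separate dose means (3 df between levels) with the straight line (1 df), leaving 2 df.

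| True pattern | Slope | 40 vs 1, pooled SD | 3-df dose-level test | 2-df lack of fit |
|---|---|---|---|---|
| Power law, 40:1 ratio 0.67 | 80% | 67% | 57% | 5% |
| Drop to 0.67 at 40 only | 19% | 67% | 67% | 63% |
| Drop to 0.67 at 1 only | 71% | 67% | 67% | 25% |
| 1.5-fold rise at 5 and 20 | 5% | 5% | 88% | 91% |
| Drop to 0.67 at 5 only | 5% | 5% | 67% | 73% |

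In the second row the regression reports the 40:1 ratio as 0.80 on average, against a true 0.67. At CV 30% the power-law row falls to 43% for the slope, 34% for the contrast and 26% for the 3-df test.

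**Group 7.** Only its first dose is comparable with the single-dose groups, and that AUC is extrapolated from 12 weeks. Under an assumed mono-exponential decline, the share beyond 84 days is 0.5^(84/15.4) = 2% at the VRC01 half-life and 0.5^(84/31) = 15% at an assumed 31 days. At 31 days the share beyond 168 days is 2%. Without Group 7, Sxx = 23.92 and the slope SE is 0.204σ instead of 0.193σ, so little precision is lost.

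**The case against.** The strongest reply is that the study is declared primarily descriptive and already has a pooled model with dose as a fixed effect, a bootstrap and a dose-normalised predictive check. The individual-subject paragraph also allows further compartmental analysis. No test or threshold is planned, so no formal false positive can arise. This largely stands, and it limits the size of the point. It does not explain why the ratios have no interval when 6.4.3 attaches one to every safety proportion, or why 1 mg/kg is left out of the listed dose effect.

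A reader might infer more than the documents support:
- **That the ratios are the only look at dose dependence.** The population model is another.
- **That the 40-fold range is wasted.** Nothing confines the ratios to adjacent doses; the 40-versus-1 contrast is available and holds 76% of the slope information.
- **That regression is one-third more precise at no cost.** The one-third figure needs a two-group SD, which the plan does not specify. Against a pooled SD the gain is 14%, and the slope assumes a constant exponent.
- **That this result decides whether IV parameters are pooled or doses extrapolated.** The overall IV summary is unconditional, and dosing simulations use the population model.

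**Conclusion.** The point holds as a modest improvement to the analysis. The linearity assessment lacks an interval and an overall estimate, and the listed population dose effect omits the lowest dose. Adding the slope narrows the interval for the 40:1 ratio by about 14% against the best ratio-based alternative and by about 33% against the crudest. This rests on a power-law relation and the planned 17 IV subjects. The factors of 1.33, 1.39 and 1.53 also rest on the VRC01 clearance CV of 19%, which is a proxy for AUC and less directly one for Cmax.

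The slope should not replace the ratios. For a change confined to 40 mg/kg, or a non-monotone pattern, it is much the weaker tool.

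**What to change.** In 6.4.5:
1. Regress log AUC0-inf and log Cmax on log dose over Groups 1, 2, 4, 5 and the first dose of Group 7. Report the slope with its 95% CI; a slope of 1 means proportionality.
2. Keep the dose-adjusted ratios, by dose level with Groups 4 and 7 combined, as a co-equal assessment with 95% CIs from a pooled SD.
3. Add a lack-of-fit check: the four dose-level means (3 df) against the straight line, leaving 2 df for departure from it.
4. Repeat the AUC analysis without Group 7, because of its 12-week extrapolation.
5. Add 1 mg/kg to the dose effect in the population model, or state why it is excluded.

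The cost is a few lines of text and one short program. No subjects, samples or visits are added. The remaining limitation is the slope's constant-exponent assumption, which items 2 and 3 are there to expose.

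### Section 6.4.5 makes no provision for carrying parameter uncertainty from about 25 subjects into the simulated target-attainment figures, although a bootstrap is already planned

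*Combined protocol and SAP*

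**What the plan says.** The population PK part of Section 6.4.5 fits one- and two-compartment models to the IV and SC data together and estimates CL, two volumes, inter-compartmental clearance and bioavailability. Two covariates are kept, "with the exception of dose (5 vs 20 vs 40 mg/kg), and first vs subsequent doses as a fixed effects on CL" and on the two volumes. Other covariates are left out for a stated reason: "Given the small subject numbers, the population PK analysis will not include an exploratory covariate analysis".

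Two further steps follow. The first checks the model: "The final population model will be assessed using bootstrap analysis and dose normalized visual posterior predictive check". The second is the dosing simulation, which "will be performed using the final population PK model and Monte Carlo simulations with at least 5000 replicates". No sentence connects the bootstrap to the simulation. The section names no resampling scheme, no target concentration, no attainment criterion and no interval to accompany an attainment percentage.

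On size, Section 6.3 plans three subjects in each of Groups 1 to 5, "and 5 subjects in each repeat dosing group (Groups 6 and 7"). It adds: "The permitted accrual is 40 subjects to allow for additional enrollments".

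**The concern.** A simulated attainment percentage carries two separate errors. One is Monte Carlo error, which shrinks as replicates are added. The other is error in the typical values and between-subject variances fed to the simulation. That error depends on how many people were studied, and no number of replicates reduces it. The replicate count is the only safeguard on precision that Section 6.4.5 attaches to this output.

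Followed as written, the plan would yield a bare percentage for each regimen. A reader comparing regimens could then take a difference of a few points as informative when the data cannot resolve it. Section 6.4.5 cites the small numbers as its reason for limiting covariates but makes no matching allowance in the simulations, although the planned bootstrap would supply what is needed.

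**Working it through.** **Inputs from the documents**
- Planned subjects (Section 6.3): 5 × 3 + 2 × 5 = 25, which agrees with the stated total. Permitted maximum: 40.
- Replicates (Section 6.4.5): at least 5000.
- Subjects by dose (Table 3): 1 mg/kg, 3; 5 mg/kg, 3 + 3 + 5 = 11; 20 mg/kg, 3 + 5 = 8; 40 mg/kg, 3.

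**Assumptions.** The plan gives neither a target nor a variability figure. I take one log-normal exposure metric per subject, its mean and SD estimated from n independent subjects, and a threshold set so that true attainment is p. The result does not depend on the CV.

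**Step 1: simulation error, p = 0.90**
- SE = √(p(1−p)/5000) = √(0.09/5000) = 0.0042.
- 95% half-width = 1.96 × 0.0042 = 0.0083, or about ±0.8 points.

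**Step 2: estimation error by the delta method**
- SE = φ(z) × √(1/n + z²/(2(n−1))), where z = 1.2816 and φ(z) = 0.1755 at p = 0.90.
- n = 25: 0.1755 × √(0.0400 + 0.0342) = 0.048.
- n = 40: 0.1755 × √(0.0250 + 0.0211) = 0.038.
- Ratio to the simulation SE: 0.0478/0.0042 ≈ 11 at n = 25, and 0.0377/0.0042 ≈ 9 at n = 40.

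**Step 3: 95% range by simulation.** The estimated mean is drawn from N(0, 1/n) and the estimated variance from χ²(n−1)/(n−1). Attainment is recomputed for each draw.

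| n | True attainment | 95% range of the estimate | Simulation error alone |
|---|---|---|---|
| 25 | 90% | 79.7 to 97.5% | ±0.8 points |
| 40 | 90% | 82.0 to 96.3% | ±0.8 points |
| 25 | 80% | 66.9 to 92.0% | ±1.1 points |

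Across assumed true attainments of 50% to 95%, the SE ratio is about 10 to 12 at n = 25 and about 8 to 9 at n = 40.

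**Step 4: what simple resampling would do.** This matters only if the bootstrap is to supply the parameter draws, and it assumes that 25 subjects are resampled without strata.
- No 40 mg/kg subject: (22/25)^25 = 4.1%.
- Exactly one distinct 40 mg/kg subject: 3 × [(23/25)^25 − (22/25)^25] = 3 × (0.1244 − 0.0409) = 25.0%.
- At most one distinct 40 mg/kg subject: 4.1% + 25.0% = 29.1%.
- Some level of the modelled dose effect (5, 20 or 40 mg/kg) absent: 4.1%, practically always the 40 mg/kg level.

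In the 4.1%, the 40 mg/kg effects on CL and the volumes cannot be estimated. In a further quarter they rest on one person. Resampling within dose and route removes the first problem entirely and reduces the second.

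**The case against.** The best defence is that the text is silent, not wrong. Simulating with the final population model does not exclude drawing its parameters from their uncertainty distribution, and no resampling scheme is named. A reader might infer that the plan fixes the parameters at point estimates, or that it specifies an unstratified bootstrap. The documents state neither. What stands is that the plan makes no provision for the uncertainty, and that it gives the bootstrap another purpose.

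Four stronger readings also fail.
- **Lost dose groups distort attainment.** As planned, the bootstrap assesses the model and does not feed the simulations, so resamples without a group cannot move the attainment figures. Stratification matters once the fix below is adopted.
- **About 12% of resamples lose a modelled dose level.** That figure counts the loss of Group 1, 2 or 5 as dose-and-route combinations. The 1 mg/kg level is not in the listed dose effect, and losing Group 2 leaves the 8 SC subjects at 5 mg/kg. For the listed effect the figure is about 4%.
- **SC attainment is only as precise as 8 subjects allow.** The model fits IV and SC data jointly, so IV subjects also inform clearance and volumes. A range computed from 8 subjects alone would overstate the uncertainty.
- **These simulations set doses in later studies.** Section 6.4.6 links later dose levels to preliminary PK analyses at each dose level, not to these simulations.

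It is also fair that Section 6.3.2 calls the study primarily descriptive, that target attainment is not a listed objective, and that the plan nowhere offers Monte Carlo error as the uncertainty of an attainment figure. These points limit the importance of the gap but do not close it.

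**Conclusion.** The point holds as a gap in specification with a concrete, better method at hand. Under the one-metric assumption, estimation uncertainty at 90% attainment is about 4.8 points of SE with 25 subjects, against 0.4 points from simulation. Enrolling the full 40 lowers it to about 3.8 points and does not remove it. The direction is robust, because replicates cannot replace subjects. The exact ratio is not, since a two-compartment mixed model with rich sampling may behave differently and the target is unknown. The resampling percentages are exact for 25 subjects under simple resampling, a scheme that the plan neither states nor rules out. This is a worthwhile improvement to a descriptive PK output. It has no bearing on the primary safety and tolerability evaluation.

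**What to change.** Add a few sentences to the population PK part of Section 6.4.5:
1. For each simulated population, draw the full parameter vector, between-subject variances included, from the bootstrap replicates or from the estimated covariance matrix. Then simulate subjects from that vector.
2. Report target attainment for each regimen with an interval that reflects those draws, not as a single percentage.
3. Resample by subject, stratified by dose level and route. State how non-converging replicates are handled and report their share.
4. State the target concentration and the attainment criterion before the simulations are run.

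The cost is SAP wording and some computing time; the bootstrap is already planned. No dose, visit or sample changes. The one visible downside is wider stated intervals. Stratification does not cure the thinness of the 40 mg/kg data: with three subjects, some replicates will still repeat one person, and the report should say so.
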